APPENDIX 2. IMPUTATION OF MISSING OR PARTIALLY MISSING DATES

In general, missing or partial dates will not be imputed at the data level. The following rules will apply for the specific analysis and summary purposes mentioned below only.

1. Prior/Concomitant Medications/Procedures

When the start date or end date of medication is partially missing, the date will be imputed to determine whether the medication is prior or concomitant. The following rules will be applied to impute partial dates for medications:

If the start date of medication is partially missing, impute as follows:

- If both month and day are missing, then set to January 01
- If only day is missing, then set to the first of the month

If the end date of medication is partially missing, impute as follows:

- If both month and day are missing, then set to December 31
- If only day is missing, then set to last day of the month

If start date or end date of medication is completely missing, do not impute. If the imputed of a medication end date > last known alive date or end of study date, then set to the last known alive date or end of study date, whichever occurs first.

2. Adverse Events

The imputation rule for the safety analyses will be used to address the issues with partial dates. When the start date or end date of an adverse event is partially missing, the date will be imputed to determine whether the adverse event is treatment-emergent. When in doubt, the adverse event will be considered treatment-emergent by default. The following rules will be applied to impute partial dates for adverse events:

If the start date of an adverse event is partially missing, impute as follows:

- If both month and day are missing, then the imputed day and month will be January 01 or the first dosing date if they have the same year, whichever is later.
- If only day is missing, then the imputed day will be the first day of the month or the first dosing date if they have the same month and year, whichever is later
- If the start date is completely missing, the imputed day will be the first dosing date as long as AE end date is not before the first dosing date.

If the end date of an AE is partially missing, impute as follows:

- If both month and day are missing, then set to December 31
- If only day is missing, then set to last day of the month

- If the end date is completely missing, do not impute.

If the imputed AE end date > last known alive date or end of study date, then set to the last known alive date or end of study date, whichever occurs first.

3. Deaths

In case complete death dates are not recorded, impute as follows:

- If both month and day are missing, then the imputed month and day will be 01Jan or the last date of a patient known to be alive + 1, whichever is later.
- If only day is missing, the death will be assumed to be on the first day of the month or the last date of a patient known to be alive +1, whichever is later.

4. Subsequent Anti-cancer Therapies

If the start date of a subsequent anti-cancer therapy is incomplete or missing, impute as follows:

- If both month and day are missing, then the imputed month and day will be 01Jan or the last day of the month for the last adequate disease assessment if they have the same year.
- If only day is missing, then the imputed day will be the first day of the month.

5. Diagnosis

If a diagnosis date is partially missing, impute as follows:

- If both month and day are missing, then set to January 01
- If only day is missing, then set to the first of the month

If a diagnosis date is completely missing, do not impute.

6. Prior Therapy/Response to Prior Therapy

If a prior therapy or response to prior therapy date is partially missing, impute as follows:

- If only day is missing, then set to the 15th of the month or the first study drug dose date, whichever is earlier. An imputed start date can be no later than the end date and vice versa.
- If month and day are missing, then set to be June 15th or the first study drug dose date, whichever is earlier. An imputed start date can be no later than the end date and vice versa.

Signature Page for VV-CLIN-125757 v1.0

Approval with eSignature	[Redacted]
--------------------------	------------

Approval with eSignature	[Redacted]
--------------------------	------------

Approval with eSignature	[Redacted]
--------------------------	------------

Approval with eSignature	[Redacted]
--------------------------	------------

Signature Page for VV-CLIN-125757 v1.0

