9.5. Timing, Frequency, and Method of Capturing Adverse Events and Serious Adverse Events

9.5.1. Adverse Event Recording Period

After informed consent has been signed but before the administration of the study drug(s), only SAEs should be reported.

After the first dose of study drug(s), all AEs and SAEs, regardless of relationship to study drug, will be reported until 40 days after last dose of study drug. All SAEs considered related to the study drug(s) that are brought to the attention of the investigator should be reported regardless of time since the last dose of treatment.

AEs and SAEs should be recorded according to the details in Table 5. For the follow-up period for AEs, see Section 9.2.4. For the definition of treatment-emergent adverse events (TEAEs), see Section 10.2.2.

Table 5: Guidance for Duration of Recording New or Worsening Adverse Events

Event Type	Record new or worsening events that occur during this period								
Event Type	Begin	End							
SAEs ^a	Signing of informed consent	Up to 40 days after last dose of study drug; initiation of new anticancer therapy, death, withdrawal of consent, or loss to follow-up, whichever comes first							
All nonserious AEs	First dose of study drug	Up to 40 days after last dose of study drug; initiation of new anticancer therapy, death, withdrawal of consent, or loss to follow-up, whichever comes first							

Abbreviations: AE, adverse event; SAE, serious adverse event.

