6.6.2. Adverse Events

AEs will be graded by investigators using CTCAE version 5.0. The AE verbatim descriptions (investigator terms from the eCRF) will be classified into standardized medical terminology using MedDRA. Adverse events will be coded to the MedDRA (Version 25.1 or higher) lowest level term closest to the verbatim term, along with the linked MedDRA preferred term (PT) and primary system organ class (SOC).

A treatment-emergent adverse event (TEAE) is defined as an AE that had onset or increase in severity level date on or after the date of the first dose of study drug through 40 days after the last dose (permanent discontinuation of study drug) or the initiation of new anti-cancer therapy, whichever is earlier. Summary tables will generally focus on those AEs that were treatment-emergent (TE). All AEs, treatment-emergent or otherwise, will be presented in patient data listings.

An AE overview table, including the number and percentage of patients with TEAEs, treatment-emergent serious adverse events (SAEs), TEAEs with Grade 3 or above, TEAEs that led to death, TEAEs that led to treatment discontinuation, TEAEs that led to dose reduction, TEAEs that led to dose interruption, TEAEs that led to dose delay, treatment-related TEAEs grade 3 or

above. Treatment-related AEs include those events considered by the investigator to be related to study drug or with a missing assessment of the causal relationship.

The incidence of TEAEs will be reported as the number (percentage) of patients with TEAEs by SOC, PT and the worst grade. A patient will be counted only once by the highest severity grade within an SOC and PT, even if the patient experienced more than 1 TEAE within a specific SOC and PT. The number (percentage) of patients with treatment-emergent SAEs, treatment-related TEAEs, TEAEs with grade 3 or above, treatment-related SAEs, TEAEs that led to death, and TEAEs that led to treatment discontinuation, dose modifications, and infusion-related reactions will be summarized by SOC and PT. TEAEs with grade 3 or above will also be summarized by PT in descending order.

Patient data listings of SAEs, fatal AEs will be provided.

All deaths and causes of death will be summarized including those occurred during the study treatment period and those reported during the safety follow-up period after treatment completion/discontinuation.

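### SAP Appendix 2: the two rules for partly missing AE start dates ignore the end date, so an SAE that resolved before dosing can be counted as treatment-emergent

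*SAP*

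**What the plan says.** SAP Appendix 2, item 2 (Adverse Events), has three rules for an incomplete start date:

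- **Day missing:** "the first day of the month or the first dosing date if they have the same month and year, whichever is later".
- **Month and day missing:** "January 01 or the first dosing date if they have the same year, whichever is later".
- **Completely missing:** "the imputed day will be the first dosing date as long as AE end date is not before the first dosing date".

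The same item sets a default: "When in doubt, the adverse event will be considered treatment-emergent by default". SAP section 6.6.2 defines a treatment-emergent AE as "an AE that had onset or increase in severity level date on or after the date of the first dose of study drug", within the 40-day or new-therapy limit, and tabulates treatment-emergent SAEs in the overview and by system organ class and preferred term.

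On collection, Protocol section 9.5.1 says: "After informed consent has been signed but before the administration of the study drug(s), only SAEs should be reported". Screening lasts at most 28 days (Protocol section 3.1, SAP section 2).

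**The concern.** Only the completely-missing rule asks whether the event had already ended. The other two take the later of two dates and stop there. If the end date is before first dose, the later date is the first dosing date, and the imputed start falls after the end. Section 6.6.2 then counts the event as treatment-emergent.

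The result is upside down: a record with no start date at all is kept off the first dosing date by the end-date condition, while a record with more information is misclassified.

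Because only SAEs are recorded between consent and first dose, the pre-dose records exposed to the rule are SAEs. Safety is a primary endpoint, and the treatment-emergent SAE count is one of its main summaries.

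**Working it through.** **Inputs.** The three start-date rules (SAP Appendix 2, item 2); the treatment-emergent definition (SAP 6.6.2); the study-day formulas (SAP 6.3.1); N = 8 (SAP section 5); a 28-day screening window. The dates below are assumed for illustration: first dose 20 June 2022, SAE end known to be 12 June 2022.

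**Step 1. The rules as written.**

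| Recorded start | Rule applied | Imputed start | Treatment-emergent? |
|---|---|---|---|
| June 2022 | max(1 June, 20 June) | 20 June | Yes |
| 2022 | max(1 January, 20 June) | 20 June | Yes |
| Completely missing | End 12 June is before 20 June, so the condition fails | None | No |

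In the first two rows the start is 8 days after the end. Under SAP 6.3.1 the start is Study Day 20 − 20 + 1 = 1 and the end is Study Day 12 − 20 = −8. A duration taken as end − start + 1 is 12 − 20 + 1 = −7 days.

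**Step 2. Is there a safeguard elsewhere?**

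- The sentence "An imputed start date can be no later than the end date and vice versa" stands only in item 6 (prior therapy). It does not reach item 2.
- The cap at the end of item 2 limits imputed end dates against last known alive or end of study. It does not limit start dates.
- The in-doubt default does not justify the result, because an event known to have ended before dosing is not in doubt. The condition in the completely-missing rule recognises this.
- Appendix 2 does not impute at the data level, and SAP 6.3.1 keeps partial dates as recorded in listings. That protects the listed start date. It does not protect the treatment-emergent flag, which is the purpose of the item 2 imputation.

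**Step 3. The same rules with the end-date condition added.** Both partial-date records (end 12 June) are not treatment-emergent, and no start is imputed to 20 June. A record with start June 2022 and end 25 June 2022 still gets max(1 June, 20 June) = 20 June and stays treatment-emergent, so the conservative intent is kept.

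**Step 4. Partial end dates.** An end recorded only as June 2022 is imputed to 30 June, which is not before 20 June. That case is truly doubtful, and the default rightly applies. An end recorded as May 2022 is imputed to 31 May, before first dose, so the added condition should cover imputed as well as known end dates.

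**Step 5. Size.**

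- One misclassified patient with no genuine treatment-emergent SAE adds 1/8 = 12.5 percentage points.
- If the patient already has one, the overall rate changes by 0, because incidence counts patients. At most a system organ class or preferred term row changes.

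**Step 6. How easily the calendar condition is met.** Assume first doses spread evenly over a 365-day year, giving 365 × 28 = 10,220 pairs of dose date and screening day.

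- Pairs in the same month: 378 for a 28-day month, 434 for a 30-day month and 462 for a 31-day month. The total is 378 + 4 × 434 + 7 × 462 = 5,348, and 5,348 / 10,220 = 52%.
- Pairs in the same year: 10,220 − (28 × 29 / 2) = 9,814, and 9,814 / 10,220 = 96%.

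The calendar match is therefore not what makes the case rare. What does is needing a pre-dose SAE, a start date that stays partial, and an end before dosing. The documents give no rate for these, so no expected count can be calculated.

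**The case against.** The strongest reply is that this will almost never happen. The exposed event starts after consent, within about 28 days of dosing. SAEs go to the sponsor within 24 hours of first knowledge (Protocol 9.5.2.1), are followed to resolution or stabilisation (9.2.4), and the data are checked for inconsistencies and completeness against source (15.1.3). Knowing the year but not the month of such an event is less plausible still. This stands, and the severity reflects it.

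The reply can add that the bias is conservative. SAP 6.3.3 intends conservative AE dates, the error can only overcount, and no hypothesis test, interim analysis or numerical safety threshold depends on the count. This also stands.

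It may further be said that since imputation serves only to decide treatment-emergence, an event with a pre-dose end needs no imputation. That is a sensible reading, but both partial-date rules are worded without any such exception, and a programmer following them will set the flag.

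Two stronger inferences are not supported. A reader might take 12.5 points as the effect of each such record; it is the upper bound. A reader might also expect negative durations to distort the safety tables, but SAP 6.6.2 plans no summary of AE duration. The conflict is confined to the derived flag, study day and any listed duration, and in a trial of 8 patients it would probably be noticed in the SAE listing.

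**Conclusion.** The two partial-date rules are wrong as written. They give an incorrect classification for a case that the SAP's own third rule handles properly, and nothing else in the SAP corrects it.

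The effect is an overcount of treatment-emergent SAEs by up to 12.5 percentage points per affected patient at N = 8, and 0 in the overall rate if that patient already counts. It requires all of the following: a pre-dose SAE, a partial start date matching the month and year (or the year) of first dose, and an end date, known or imputed, before first dose. The conclusion assumes that the rules are programmed literally and that queries leave the start date incomplete.

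The documents do not support reading this as a general flaw in the safety analysis. It is a minor correction that is worth making because it costs almost nothing.

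**What to change.** In SAP Appendix 2, item 2, extend the end-date condition to both partial-date rules. For example: if the AE end date, recorded or imputed, is before the first dosing date, the event is not treatment-emergent, and a partial start date is left as recorded and not set to the first dosing date. Add that an imputed AE start date may not be later than the AE end date.

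Do not fall back to the first of the month or January 01 for these events. SAEs are recorded only from consent, and in the example the earliest screening day is 23 May (20 June less 28 days). A start of 1 January would be 142 days before that, which replaces an impossible duration with a false one. Leaving the date partial avoids this, since the flag can be set from the end date alone.

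The cost is one sentence in the SAP and one condition in the program. Data collection and the protocol do not change.

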6.5. Efficacy Analysis

6.5.1. Efficacy Endpoint(s)

The analysis of event free survival (EFS) is based on the safety analysis set. EFS is defined as the time from initiating study drug(s) to disease progression, death from any cause, relapse, secondary malignancy as assessed by investigators. The distribution of EFS, including median, Q1 and Q3, and event-free rates at the 6th month, will be estimated using the Kaplan-Meier

method for each treatment group. Ninety-five percent CIs for median and Q1 and Q3 of EFS will be estimated using the method of Brookmeyer and Crowley ([Brookmeyer and Crowley, 1982](#)), and 95% CIs for event-free rates will be estimated using Greenwood's formula ([Greenwood, 1926](#)).

The censoring rules for the primary analysis of EFS are presented in [Table 1](#).

Table 1: Handling of Intercurrent Events and Missing Values of Event Free Survival

	Derivation rules	Outcome
No event at the time of data cut-off or withdrawal from study or lost to follow up	Date of last adequate radiologic assessment prior to or on date of data cut-off or withdrawal from study	Censored
Intercurrent events		
Discontinuation of the treatment	Tumor assessment data collected after discontinuation of study treatment will be used for analysis (treatment policy strategy)	No impact
New anticancer therapy started prior to EFS events.	Last adequate disease assessment before the new anticancer therapy (hypothetical strategy)	Censored
Missing values not related to intercurrent events		
Patients' withdrawal from the study or lost to follow-up	Last adequate disease assessment prior to patient withdrawal from the study (hypothetical strategy)	Censored
No baseline or post-baseline disease assessments without death	Date of the first dose	Censored
disease assessments with death	Date of death	Event

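### A new anticancer therapy with only the day missing is dated to the 1st of the month with no anchor, so a documented progression in that month can become a censored EFS time

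*SAP*

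**What the plan says.** SAP Appendix 2 item 4 (Subsequent Anti-cancer Therapies) has two rules. When month and day are both missing, the date is "01Jan or the last day of the month for the last adequate disease assessment if they have the same year"; which of the two applies is not stated. When only the day is missing, the rule is "If only day is missing, then the imputed day will be the first day of the month", with no second date to compare against.

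Two neighbouring rules in the same appendix are anchored. A death with the day missing is placed on "the first day of the month or the last date of a patient known to be alive +1, whichever is later". An AE start with the day missing is placed on "the first day of the month or the first dosing date if they have the same month and year, whichever is later".

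Two analyses depend on the therapy start date:

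- **EFS.** SAP 6.5.1 Table 1 lists "New anticancer therapy started prior to EFS events" as an intercurrent event. Such a patient is censored at the last adequate assessment preceding that therapy.
- **TEAEs.** SAP 6.6.2 runs the window "through 40 days after the last dose (permanent discontinuation of study drug) or the initiation of new anti-cancer therapy, whichever is earlier". Protocol 10.2.2 has the same limit.

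Scheduled tumour assessments are few: screening, end of Cycle 3 and the EOT Visit (SAP section 2).

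**The concern.** The day-missing rule always picks the earliest possible day. A patient who progresses and starts another therapy later in the same month would be recorded as having started it before progressing. Table 1 would then treat a real event as a censoring and move the patient's time back to an earlier scan. For progression and relapse this error can only favour the drug.

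The rule also sits oddly beside its sibling. On the natural reading, losing both month and day gives a date at the end of the assessment month, which keeps the event. Losing only the day gives a date at the start of the month, which loses it. Less information should not give the better answer.

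A start date imputed before the last study dose could also close the TEAE window while the patient was still on treatment, and TEAEs feed a primary endpoint.

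**Working it through.** The plan states no figure on this point, so there is nothing to reproduce. The check applies the rules as written.

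**1. Worked dates (assumed).** Last dose 6 March, progression 10 March, true therapy start 20 March, recorded with the day missing.

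- Imputed start: 1 March, before both the progression and the last dose.
- EFS: the 10 March event becomes a censoring at the last adequate assessment before 1 March. On schedule that is end of Cycle 3, or screening if there is nothing later.
- TEAE window with the true date: the earlier of 15 April (last dose + 40) and 20 March, so 14 days after last dose.
- TEAE window with the imputed date, if it is used there: 1 March, so 5 days before last dose.
- If month and day were both missing and the later date of that rule is taken: 31 March, and the event is kept.

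**2. How often the order is reversed, given a missing day.** Assume progression is equally likely on each day of a 365-day year and therapy truly starts g days later. The imputed date precedes progression only if both fall in the same month and progression is not on the 1st. In a month of m days that leaves max(0, m − g − 1) progression days, so:

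share = Σ over 12 months of max(0, m − g − 1) / 365

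| Lag g (days) | Calculation | Share |
|---|---|---|
| 7 | (365 − 12×8)/365 = 269/365 | 74% |
| 14 | (365 − 12×15)/365 = 185/365 | 51% |
| 21 | (365 − 12×22)/365 = 101/365 | 28% |
| 28 | (7×2 + 4×1 + 0)/365 = 18/365 | 5% |
| 30 or more | 0/365 | 0% |

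The same shares apply with last dose in place of progression. With the anchors proposed below, the share is 0 at every lag.

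**3. Effect on the 6-month EFS rate.** n = 8 (SAP section 5); 6 months = 6 × 30.4375 = 182.6 days (SAP 6.3.2). Assumed: events on day 140, and on day 150 where there are two; other patients followed event-free to day 190; the recoded patient censored on day 105 (end of Cycle 3, 3 × 35). Intervals are Greenwood 95%, capped at 100%.

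- One event: S = 7/8 = 87.5%; SE = 0.875 × √(1/56) = 0.117; interval 64.6 to 100%. Recoded: no events, S = 100%.
- Two events: S = 7/8 × 6/7 = 75.0%; SE = 0.75 × √(1/56 + 1/42) = 0.153; interval 45.0 to 100%. First event recoded: S = 6/7 = 85.7%; interval 59.8 to 100%.

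One recoded patient therefore adds 12.5 or 10.7 percentage points.

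**The case against.** The case for leaving the rule alone has five parts.

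- **The trigger may never occur.** The percentages require a missing day and a short lag, and the documents give no rate for either. With about 8 patients at 1 to 3 centres, a Safety Follow-up Visit timed before any new therapy (Protocol 7.5.1), the reason for stopping recorded (7.6.1) and data reviewed for logic and inconsistency (15.1.3), a partial date is unlikely and a reversed one should be queried. This stands as a limit on frequency. It does not make the rule right when the day cannot be retrieved, which is the only case the rule serves.
- **The TEAE effect is uncertain.** Appendix 2 limits its rules to stated purposes; item 4 states none, and its only anchor is a disease assessment, which points to EFS. Item 2 treats doubtful AEs as treatment-emergent, and SAP 6.6.2 lists every AE. This largely stands. The doubt default is written for partial AE dates, however, and does not clearly reach a complete AE date set against an imputed therapy date.
- **EFS is exploratory.** There is no hypothesis test, and both shifted estimates lie inside the unshifted intervals. This stands.
- **A floor at the event date is not neutral.** It uses the outcome to order the intercurrent event and would count as events some patients whose therapy truly came first. This stands and shapes the fix.
- **Overlap with study drug is foreseen.** Protocol 7.6.1 lists concurrent anticancer therapy as a reason to stop study drug, so a start before last dose is not impossible. This also stands.

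**Conclusion.** The defect is real but narrow. Read with Table 1, the day-missing rule can reverse the order of a documented progression or relapse and a later therapy in the same month. It then censors a true EFS event, always in the favourable direction. No section of the SAP or protocol prevents this, and the comparable rules for deaths and AE starts are anchored.

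The size depends on three assumptions: a missing day, the lag (74% reversed at 7 days, falling to 0% at 30 or more) and the number of events among 8 patients. No planned test or interim decision rests on EFS.

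A reader might infer that most progressions would be lost, or that on-treatment AEs will disappear from the primary safety results. The documents support neither. The percentages are conditional and say nothing about how often a day will be missing. The safety effect arises only if item 4's date is also used for the TEAE window, which the SAP does not say; even then the AEs leave the summary tables and stay in the listings.

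**What to change.** Query the site for the day first. In SAP Appendix 2 item 4, when only the day remains missing, impute the latest of:

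- the 1st of the month;
- the day after the last study-drug dose;
- the day after the last adequate disease assessment or documented progression or relapse.

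Use only anchors in that same month and year, and cap the result at the earlier of month end and the date of death. If the cap puts therapy on the event date, the event is kept, because a same-day start is not prior to it. In the worked example this gives 11 March: the progression counts, and the TEAE window would end 5 days after last dose.

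State that this is a default. Where the records show that therapy began before the event or overlapped study drug, keep the documented order. State also whether the imputed date applies to EFS censoring, the TEAE window or both.

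Leave the month-and-day-missing rule as it is, except to say that the later of its two dates applies. The same floor cannot be carried over, because its anchors are chosen by a month that is then unknown.

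The cost is a short SAP edit and minor programming, with no new data. The downside is that a few truly earlier but undocumented therapy starts would be counted as EFS events, which is the less favourable direction for the drug.
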